## 2.1 Primary brain tumors

Primary brain tumors are the most common primary brain tumor in the United States, and despite aggressive multimodal therapy with maximum safe resection, radiotherapy in combination with concurrent and adjuvant temozolomide, the median survival of the most aggressive form of primary brain tumor, glioblastoma, in clinical trial populations is **16 months**. There has been an unfortunate stagnation in the ability of non-invasive diagnostics to accurately differentiate between treatment response and failure. Even under optimal circumstances with the use of 'state of the art' diagnostic and therapeutic interventions, less than 15% of patients will survive five years. [8] [9] [10] While the introduction of temozolomide into the first-line standard of care [11] achieved some survival improvement, nearly all patients relapse and treatment options for recurrent disease remain limited and largely ineffective.

The ability to measure the response to treatment is a critical component in evaluating the efficacy of new therapies. Unfortunately, current diagnostic neuroimaging paradigms fail to evaluate treatment response for glioblastoma reliably. The initial landmark imaging evaluation guidelines – the Macdonald criteria – were established in 1990 and was based solely on the assessment of contrast-enhancement as a surrogate for tumor size. Contrast-enhancement is non-specific and reflects the degree of extravasation of a contrast agent across a disrupted blood-brain: changes in contrast-enhancement may be attributable to real progression, imaging technique, treatment (surgery, radiation, or chemotherapy), steroids and parenchymal changes unrelated to the tumor (postsurgical changes, ischemia, seizures). Particularly with the use of multimodal therapy with radiation and temozolomide and new systemic therapies such as bevacizumab, new radiological

phenomena including pseudoprogression and pseudoresponse have added further complexity to assessing treatment response.

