## 4.6 Imaging Time Points

4.6.1 A single research imaging session will be planned for each patient. However, patients will still undergo follow-up imaging scans as part of their standard of care. These follow-up scans will serve as the basis for statistical analyses that consider treatment response or disease recurrence.

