## 7 STATISTICAL CONSIDERATIONS

### 7.1 Definitions

7.1.1 Lesion “**treatment response**” will be defined by size and contrast to noise ratio (CNR). Treatment response will be assessed only in patients with treatment prior to enrollment.

7.1.1.1 Size – treatment response in a single lesion will be considered as a decrease in size of 30%. (see section 5.1)

7.1.1.2 CNR—treatment response will be considered as a decrease in T1 post-contrast CNR of at least 20%. (see section 5.2) by standard T1 post-contrast imaging.

7.1.1.3 Lesions that do not meet these criteria for treatment response will be considered treatment failure.

7.1.2 Disease **recurrence** will be determined by surgical pathology (if available) or at least three months of imaging follow-up. Disease recurrence will be assessed only in patients with treatment prior to enrollment. Imaging findings will be considered recurrent disease in a lesion if:

7.1.2.1 The lesion was initially considered to be a treatment responder.

7.1.2.2 The lesion showed a successive increase in the size of 25% from nadir or a single imaging time point increase of 40%. (see section 5.1)

7.1.2.3 Lesions that do not meet these criteria will be considered radiation necrosis.

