## 7.4 Analysis Plan

Patients with metastasis are expected to have on average 2-3 detectable brain lesions each. Patients with primary brain tumors are expected to have a single lesion. All analyses will be performed on the largest lesion within patients, and some analyses will be repeated on a per-lesion basis.

The CNR for each imaging method will be determined and reported along with the corresponding 95% confidence interval. In secondary analyses, for the conspicuity endpoints, the T1 sequence by MRI will be considered the gold standard, and we will compare the conspicuity of each of the other methods to that of T1 sequencing by using McNemar's test. This analysis will first be performed in the largest lesion per patient, and then analyses will be repeated using all lesions.

If enough follow-up images are obtained (see section 4.5), we will compare the CNR in lesions that respond to treatment to those that do not by using a Wilcoxon rank-sum test. We will compare the CNR between baseline and follow-up within patient by using a Wilcoxon signed-rank test. Also, for those lesions that initially respond, some will subsequently grow in size after the initial response. Of these, some will be considered radiation necrosis and some progressive disease. The CNR will be compared between lesions with necrosis and those that are progressive disease using a Wilcoxon rank-sum test.

Exploratory aims will be analyzed with descriptive statistics. fMRI paradigms will be summarized by the group mean and standard deviation. Patient satisfaction will be reported on a five-point Likert scale and compared between the 7T scan and the most recent clinical scan by using a Wilcoxon rank-sum test.

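### The recurrence/necrosis label has a three-month minimum but no common read time, so for lesions without pathology it depends partly on how long routine imaging happened to continue

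*Combined protocol and SAP*

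**What the plan says.** Section 7.1.2 applies to patients treated before enrolment. Recurrence "will be determined by surgical pathology (if available) or at least three months of imaging follow-up". On imaging, two conditions must be met. The first is prior response (7.1.2.1): "The lesion was initially considered to be a treatment responder". The second is growth (7.1.2.2): "The lesion showed a successive increase in the size of 25% from nadir or a single imaging time point increase of 40" per cent. Section 7.1.2.3 closes the rule: "Lesions that do not meet these criteria will be considered radiation necrosis".

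The study itself makes one scan. Section 4.6.1 states that "patients will still undergo follow-up imaging scans as part of their standard of care", and "These follow-up scans will serve as the basis for statistical analyses that consider treatment response or disease recurrence". Section 4.7 ends participation at the study scan, on request or at death. No section gives a scan schedule, a maximum follow-up, a common assessment date, or a label for a lesion whose imaging stops early.

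Section 7.4 uses the label as follows: "The CNR will be compared between lesions with necrosis and those that are progressive disease using a Wilcoxon rank-sum test". The sentences just before it describe lesions that first responded and later grew, and divide those into necrosis and progressive disease. These follow-up analyses are conditional on there being enough follow-up images; what counts as enough is not defined.

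**The concern.** Regrowth accrues over time, but the rule reads it as yes or no over whatever routine imaging exists beyond month 3. Two lesions with the same biology can get opposite labels because one patient was scanned for three months and the other for two years. The default works in one direction: everything not yet shown to be recurrent becomes necrosis, including lesions for which imaging stopped too early to tell.

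A longer minimum alone would not cure this, because follow-up would still be unequal and open-ended.

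At stake is the only test in Section 7.4 that contrasts necrosis with progressive disease, which is the contrast named in the secondary objective (Section 1.2). If progressive lesions sit in the necrosis group, the CNR difference between the groups shrinks, and a modality that separates the two conditions could look as if it does not.

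**Working it through.** **The plan's own calculation.** The only one is CI precision for CEST CNR (Section 7.3: mean 14.9, SD 3.0). 14.9 ± 1.96 × 3.0/√20 = 13.585 to 16.215, and with n = 45, 14.023 to 15.777. Both match the stated 13.6 to 16.2 and 14.0 to 15.8. This concerns the primary estimates. The plan gives no regrowth time, follow-up distribution, effect size or evaluable number for the necrosis comparison.

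**What the text fixes.** Without pathology:
- Growth reaches the 25%/40% threshold after prior response: recurrence.
- Imaging ends after month 3 with growth below threshold: necrosis under 7.1.2.3, and inside the set that 7.4 describes if the lesion had responded.
- Imaging ends after month 3 with no recorded growth: necrosis under 7.1.2.3, but outside the set that 7.4 describes.

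**Illustration on the literal reading of 7.1.2.3.** Assumptions, none from the plan except the survival figure:
- Time from the 7T scan to qualifying regrowth is exponential with median m = 3, 6, 12 or 18 months.
- Section 2.1 gives "the median survival of the most aggressive form of primary brain tumor, glioblastoma", as 16 months in clinical trial populations. It is applied here to everyone from the 7T scan, exponential and independent of regrowth.
- Imaging is otherwise available for a time uniform over 3 to 36 months.
- There is no pathology, and every lesion passes the responder condition.

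*Follow-up length alone.* The share of true recurrences not yet past threshold at time T is exp(−ln2 × T/m):

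| m (months) | T = 3 | T = 12 | T = 24 |
|---|---|---|---|
| 3 | 50% | 6% | 0.4% |
| 6 | 71% | 25% | 6% |
| 12 | 84% | 50% | 25% |
| 18 | 89% | 63% | 40% |

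*Adding death and unequal follow-up.* Let a = ln2/m, b = ln2/16 = 0.0433, c = a + b and K = (1 − e^(−33c))/(33c). Among patients with at least three months of follow-up, the share labelled necrosis is e^(−3a) × [b(1 − K)/c + K]. The first term is death first; the second is imaging ending first.

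| m | K | death first | imaging ends first | total |
|---|---|---|---|---|
| 3 | 0.110 | 0.070 | 0.055 | 0.125 |
| 6 | 0.190 | 0.156 | 0.134 | 0.290 |
| 12 | 0.289 | 0.256 | 0.243 | 0.499 |
| 18 | 0.345 | 0.309 | 0.308 | 0.616 |

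*Dilution.* Assume also that half the lesions are truly progressive and that mislabelled lesions have the same CNR as other progressive ones. If a share s is mislabelled, the necrosis group contains s/(1 + s) progressive lesions, and the mean difference falls to 1/(1 + s) of its true size: 89% at s = 0.125 and 62% at s = 0.616.

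**Does a common read time help?** Take m = 12 and read time H, and let h = H − 3.
- Share still without a criterion at H or at the end of imaging: e^(−3a) × (b + aJ)/c, where J = [(1 − e^(−ch))/c + (33 − h)e^(−ch)]/33.
- Share imaged to H without a criterion (called non-progressive): e^(−aH) × e^(−bh) × (36 − H)/33.
- The difference between the two is indeterminate.

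| H | progressive | non-progressive | indeterminate | non-progressive among labelled |
|---|---|---|---|---|
| 6 | 0.279 | 0.565 | 0.156 | 67% |
| 12 | 0.413 | 0.246 | 0.341 | 37% |
| 24 | 0.492 | 0.037 | 0.471 | 7% |

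All of these lesions are true recurrences, so the last column is the error among labelled lesions. Under the present rule it is 50%. A 6-month read time is worse and a 24-month one much better, at the price of 47% indeterminate.

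**The case against.** The strongest reply is that Section 7.4 limits its comparison to lesions that responded and then grew. A reader might infer from 7.1.2.3 that every patient who dies after month 3 without regrowth is counted as necrosis in the rank-sum test. The documents do not support that. The definition never mentions death; the label follows only from the default, and on 7.4's wording a lesion with no growth may carry it without entering the test. This stands. It does not help a responding lesion that had grown below threshold when imaging stopped, which enters as necrosis on either reading.

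The illustration can also be challenged:
- It leaves out pathology, which the plan puts first, and the responder condition.
- Treated patients enter with new or increasing signal (Section 3.1), so short regrowth times are plausible, and at a 3-month median only about one lesion in eight is mislabelled.
- The survival figure is for glioblastoma, whereas about half of the treated patients are expected to have metastases (Section 7.3).
- Death is taken as independent of regrowth.

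These points stand, so the percentages show a range and are not estimates for this trial. A reader might also want to state a loss of power. The documents give no effect size and no number of evaluable lesions for this comparison, so no such figure can be supported.

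Finally, a read time is no cure in itself: a short one increases mislabelling, and excluding early deaths selects on survival. Both are true and shape the fix.

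**Conclusion.** The point holds in limited form. The three-month floor combined with the default to necrosis makes the label of lesions without pathology depend partly on length of imaging. This follows from the rule as written, and no other section corrects it. It certainly reaches the 7.4 comparison through lesions with sub-threshold growth at their last scan; whether it also does so through lesions with no recorded growth depends on how 7.1.2.3 and 7.4 are reconciled.

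The expected consequence is a diluted CNR difference between necrosis and progression, provided that mislabelled lesions resemble other progressive ones. Its size cannot be derived from the documents. The 12.5% to 62% range applies to the literal reading only and rests on the assumed regrowth medians, follow-up distribution and mortality. The primary CNR estimates and their confidence intervals are unaffected, and the comparison is a conditional one serving the secondary objective. The change is worth making, but it does not threaten the study's main result.

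**What to change.** 1. Replace the default in 7.1.2.3. A lesion without pathology and without a qualifying criterion is called necrosis (non-progressive) only if it has an evaluable scan at a prespecified common read time after the 7T scan. Otherwise it is indeterminate and left out of the main comparison.
2. Fix that read time before any labels are read, set it clearly longer than the three-month minimum, and repeat the comparison at one or more other read times, because the result depends on the choice.
3. Add a sensitivity analysis that counts deaths before the read time as progressive.
4. Reconcile 7.1.2.3 with 7.4 on which lesions enter the comparison: all labelled lesions, or only those that responded and then grew.

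Cost: revised wording and one derived variable from scans already made in routine care, with no extra imaging. Fewer lesions will be labelled. At an assumed 12-month regrowth median, about 16%, 34% and 47% of true recurrences would be indeterminate at read times of 6, 12 and 24 months. Leaving them out brings some selection on survival, which item 3 addresses and the report should state.

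### On imaging alone, 7.1.2.3 makes radiation necrosis the residual label for treated lesions; 7.4 tests a narrower set, which can still include never-irradiated lesions and omits progression without prior response

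*Combined protocol and SAP*

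**What the plan says.** Section 7.1.1.3 gives every treated lesion that misses the response criteria a label: "Lesions that do not meet these criteria for treatment response will be considered treatment failure".

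Section 7.1.2 then deals with recurrence. Its population is all previously treated patients: "Disease recurrence will be assessed only in patients with treatment prior to enrollment". Status "will be determined by surgical pathology (if available) or at least three months of imaging follow-up". On imaging there are two criteria. The first, 7.1.2.1, is "The lesion was initially considered to be a treatment responder". The second, 7.1.2.2, is "The lesion showed a successive increase in the size of 25% from nadir or a single imaging time point increase of 40" per cent. Section 7.1.2.3 closes the list: "Lesions that do not meet these criteria will be considered radiation necrosis". It has no condition on response, growth or prior radiation.

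Section 7.4 opens its follow-up analyses with "If enough follow-up images are obtained". It compares CNR between responding and non-responding lesions by a rank-sum test. It then takes up necrosis: "for those lesions that initially respond, some will subsequently grow in size after the initial response". Those lesions are split into radiation necrosis and progressive disease and compared by a second rank-sum test.

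Two other places matter. Section 3.1 admits treated patients whose prior treatment was surgery, radiation, chemotherapy or immunotherapy, so radiation is not required. Secondary objective 1.2.1 concerns telling radiation necrosis from progressive disease and does not restrict this to lesions that first responded.

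**The concern.** A residual category is safe only if everything that falls into it deserves the name. Here the residual is a specific diagnosis. Taken literally, 7.1.2.3 gives it to three kinds of lesion that have no evident claim to it: non-responders that go on growing, responders that never regrow, and lesions that were never irradiated.

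The second rank-sum test is the only comparison in 7.4 between necrosis and progressive disease, which is the distinction named in 1.2.1. If the necrosis group contains lesions that cannot be radiation necrosis, the CNR contrast no longer measures what the objective asks. If the progressive group excludes progression without prior response, the result covers less than the objective states. In addition, 7.1.2.3 and 7.4 describe different necrosis populations, so an analyst who built the groups from the 7.1.2 labels alone would not get the groups that 7.4 describes.

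**Working it through.** The check is an enumeration of labels. The plan gives no sample size or precision figure for this comparison, so there is no stated figure to reproduce.

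**Inputs.** Response yes or no (7.1.1); later size course, in three levels: growth meeting 7.1.2.2, growth below it, no growth; the residual rule (7.1.2.3); the test population (7.4); treatment types (3.1).

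**Assumptions.** No pathology and at least three months of imaging follow-up. Criteria 7.1.2.1 and 7.1.2.2 are joined by AND. The text does not state the connective, but this is the natural reading.

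**Step 1: labels under 7.1.** Combinations: 2 × 3 = 6.

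| Response | Later size course | 7.1.1.3 label | 7.1.2 label | In 7.4 necrosis test |
|---|---|---|---|---|
| Yes | Meets 7.1.2.2 | – | Recurrent | Yes |
| Yes | Growth below it | – | Necrosis | Yes |
| Yes | No growth | – | Necrosis | No |
| No | Meets 7.1.2.2 | Failure | Necrosis | No |
| No | Growth below it | Failure | Necrosis | No |
| No | No growth | Failure | Necrosis | No |

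Recurrent: 1. Necrosis: 6 − 1 = 5. Of the 5, 3 are also treatment failure, and 1 of those 3 has growth meeting 7.1.2.2.

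Example of that last row type: a lesion that fails both the size and the CNR response criteria and goes from 20 mm to 40 mm at the next time point. Growth is 40/20 − 1 = 100%, which is 100/40 = 2.5 times the single-time-point threshold. It is labelled both treatment failure and radiation necrosis.

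**Step 2: what reaches the test.** The 7.4 population is responders with any later growth: 2 of 6, one recurrent and one necrosis. The 4 left out (1 responder without regrowth, 3 non-responders) all carry the necrosis label. So 5 − 4 = 1 necrosis combination enters the test, and the 20 to 40 mm example does not.

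**Step 3: prior radiation.** Splitting each row by irradiated yes or no gives 6 × 2 = 12 combinations, of which 5 × 2 = 10 are labelled necrosis and 5 of those were never irradiated. In the 7.4 population there are 2 × 2 = 4. Two of them are labelled necrosis, and 1 of those 2 was never irradiated.

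**Step 4: the OR reading.** If either criterion sufficed, all 3 responder rows and the non-responder row meeting 7.1.2.2 would be recurrent (4), leaving 2 necrosis rows, both non-responders. The 7.4 population would then hold no imaging-defined necrosis lesion and the test would lose a group. This supports AND as the intended reading.

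**The case against.** The strongest reply is that most of the mislabelling never reaches a specified analysis. Section 7.4 takes only responders that later grow, and within that set 7.1.2 gives each lesion a single label. This stands. A reader might infer from 7.1.2.3 that the tested necrosis group will be filled with progressing non-responders; the plan does not support that, because it would require ignoring 7.4.

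A second reply is that 7.1.2.3 was meant only for responders that regrow, since non-responders already have a label in 7.1.1.3. That reading would match 7.4 and remove the population conflict. It is plausible, but 7.1.2.3 does not say it, and it does not deal with lesions that were never irradiated or with the wider scope of 1.2.1.

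Third, non-responders are not lost to analysis: they enter the separate responder versus non-responder comparison. This also stands. They are missing only from the necrosis contrast.

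Fourth, 7.1 does not define progressive disease, and a reader might conclude that one arm of the test is undefined. The term most likely means recurrence as set out in 7.1.2, so the difference is editorial. Section 3.1 does attach treatment failure to progressive disease, but there it describes a suspicion at enrolment, not a lesion class for analysis.

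**Conclusion.** The point holds in a limited form. The residual rule in 7.1.2.3 conflicts with 7.1.1.3 and is wider than the 7.4 population. In the test as specified, two faults remain: a never-irradiated regrown responder can be counted as radiation necrosis, and progression without initial response is absent although 1.2.1 sets no such limit.

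This rests on the AND reading, no pathology, and at least three months of follow-up. Where pathology is available it can settle status instead. The counts describe label combinations and depend on the grid chosen; they are not lesion frequencies, and the documents give no basis for estimating those.

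The reach is modest. The test is secondary and depends on enough follow-up images. The primary CNR estimates are grouped by tumour type and treatment status and do not use these labels. One might infer that the McNemar conspicuity analysis is either affected or safe; neither can be shown, because 7.4 does not say how conspicuity is scored. The wording should be fixed before the follow-up lesions are classified.

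**What to change.** Reconcile 7.1.1.3, 7.1.2.3, 7.4 and 1.2.1:

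- Limit 7.1.2.3 to the population that 7.4 tests, so that no lesion is both treatment failure and radiation necrosis, and lesions that do not grow are not called necrosis by default. State that 7.1.2.1 and 7.1.2.2 are both required, if that is the intent.
- Record prior radiation for each lesion, and keep never-irradiated lesions out of the radiation necrosis group.
- Use one term, recurrence or progressive disease, in both 7.1.2 and 7.4.
- Either state in 1.2.1 that the comparison is limited to initial responders, or have the investigators define how growing non-responders enter it.
- Report the number of lesions in each category, including those that cannot be assigned.

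The diagnostic criteria themselves are for the investigators to set.

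The cost is wording plus one history item per lesion. Follow-up comes from the standard-of-care scans already relied on in 4.6.1, so no research scan is added. The drawback is that some lesions leave the necrosis group, which leaves fewer for a comparison that already depends on enough follow-up.

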## 7.2 Overview

Patients with untreated disease (new lesions) will be categorized as having brain metastasis, primary brain tumor, or non-tumor based upon the following:

1. Patients with well-defined intra-axial lesions seen in the setting of pathology-proven solid organ malignancy will be considered metastasis.
2. Patients without history of a primary malignancy and agreement on a likely diagnosis of primary brain tumor by both a neurosurgical and neuroradiology co-investigator will be considered primary brain tumor.
3. Patients that do not the above criteria will be categorized as having non-tumor.

Patients in categories 1 and 2 will be further classified as having received treatment and not having received treatment.

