## 2.7 Protocol Particular Disease Description

Brain malignancy will be defined as suspected or pathologically proven space-occupying intra-axial lesion. Suspected (not pathologically proven) brain malignancy will require confirmed suspicion from a neurosurgery and neuroradiology collaborator.

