## 3 ELIGIBILITY

### 3.1 Inclusion Criteria

#### Patients

- 13 years old and above.
- Written Informed consent must be obtained by the patient (age 13-17)'s parent or legally authorized representative (LAR)
- Patients must meet one set of inclusion criteria:
  - Newly identified and untreated primary brain tumor or metastasis of at least 5 mm or greater in size.
    - Suspected central nervous system neoplasms will require agreement from a study neuroradiologist and a study neurosurgeon, neuro-oncologist, or a radiation oncology that a lesion exists that is most likely either a primary brain tumor or a metastasis.
    - Patients with suspected brain metastasis must also have a history of solid organ malignancy.
  - History of primary brain tumor or metastasis treated with surgery, radiation, chemotherapy, or immunotherapy with new or increasing signal on MR imaging that is suspicious for progressive disease (treatment failure).
    - Suspected recurrent neoplasms will require agreement from a study neuroradiologist and a study neurosurgeon, radiation oncologist, or neuro-oncologist that lesion behavior is suspicious for recurrent disease.

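### Section 7.2, the only rule that forms the tumour-type groups for the primary objective, misassigns some eligible untreated patients if followed literally and is contradictory for treated patients

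*Combined protocol and SAP*

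**What the plan says.** Section 1.1.1 asks for CNR separately by malignancy type and treatment status. Section 7.3 divides patients into five groups by pointing back to 7.2, and 7.2 is the only place where type is assigned. Its list begins: "Patients with untreated disease (new lesions) will be categorized as having brain metastasis, primary brain tumor, or non-tumor". The three rules are:

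- Rule 1: "Patients with well-defined intra-axial lesions seen in the setting of pathology-proven solid organ malignancy will be considered metastasis". The pathology condition attaches to the organ cancer, not to the brain lesion.
- Rule 2: "Patients without history of a primary malignancy and agreement on a likely diagnosis of primary brain tumor", the agreement being between a neurosurgical and a neuroradiology co-investigator.
- Rule 3: "Patients that do not the above criteria will be categorized as having non-tumor" (a verb appears to be missing; the sense is clear).

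The section then adds: "Patients in categories 1 and 2 will be further classified as having received treatment and not having received treatment".

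Eligibility is set elsewhere. Section 3.1 admits "Newly identified and untreated primary brain tumor or metastasis of at least 5 mm or greater in size". It sets a size but no margin criterion and does not bar a history of another cancer. For a suspected new lesion it asks for "agreement from a study neuroradiologist and a study neurosurgeon, neuro-oncologist, or a radiation oncology" that the lesion is probably one of the two tumour types, without asking which. Section 2.7 covers both suspected and pathologically proven lesions and says that an unproven one "will require confirmed suspicion from a neurosurgery and neuroradiology collaborator". Treated patients enter under 3.1 through a history of a treated primary brain tumour or metastasis.

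**The concern.** The groups are the strata of the primary objective, so a rule that puts a patient in the wrong stratum acts directly on the primary estimates. No rule in 7.2 requires the brain lesion's own established diagnosis to be used. Rule 2's likely diagnosis may draw on pathology, but pathology cannot override its no-prior-malignancy condition, and it plays no part in rule 1.

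Two effects follow. Wrong patients enter a tumour group, which can shift its mean CNR. Genuine tumours leave for group 5, which costs some precision. Section 7.4 plans no analysis specific to group 5, so its content matters mainly through the tumours it takes from the four reported groups. It is nevertheless not simply the set of mimics that 7.3 assumes; it is whatever the first two rules leave over.

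Timing adds to this. Section 7.2 does not say when patients are categorized or whether later pathology moves them. Section 3.2 excludes surgical treatment between the diagnostic and the study MRI, so resection pathology of a new lesion can come only after the scan, although a biopsy may come earlier.

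**Working it through.** **The rules applied literally to eligible patient types**

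| Patient | Rule 1 | Rule 2 | Assigned |
|---|---|---|---|
| Typical metastasis, well-defined, proven solid organ cancer | met | – | metastasis (correct) |
| Typical primary tumour, no cancer history, both specialists agree | not met | met | primary (correct) |
| Pathology-proven glioma, well-defined, earlier solid organ cancer | met | barred by history | metastasis |
| The same, not well-defined | not met | barred by history | non-tumor |
| Primary brain tumour, earlier haematologic malignancy | not met | barred by history | non-tumor |
| Metastasis judged not well-defined | not met | barred by history | non-tumor |
| Well-defined stroke or demyelinating lesion, proven solid organ cancer | met | – | metastasis |

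The common cases are assigned correctly; the last five are not.

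**Treated patients.** Section 7.3 expects about half of each tumour type to be treated. If the opening sentence of 7.2 governs, the rules do not cover them. If the closing sentence governs, they do, and a treated primary brain tumour is primary or non-tumor according to whether it counts as its own earlier malignancy. Section 3.1 supplies their tumour history, but 7.2 does not refer to it.

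**The plan's own figures (7.3: mean CEST CNR 14.9, SD 3.0).** Half-width = 1.96 × SD/√n.

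- n = 20: 1.96 × 3/√20 = 1.31, giving 13.6 to 16.2, as stated.
- n = 45: 1.96 × 3/√45 = 0.88, giving 14.0 to 15.8, as stated.
- Group size: 100 × 0.90/4 = 22.5, within the stated 20 to 25.

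**Illustration of misassignment.** Let f be the misassigned fraction of a group and d the CNR shift of those patients, of either sign. The documents give neither, so both are assumed. Bias b = f × d; SD = √(9 + f(1−f)d²); se = SD/√n; coverage of the 95% interval = Φ(1.96 − b/se) − Φ(−1.96 − b/se).

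| f | d | b | SD | Coverage, n=20 | Coverage, n=45 |
|---|---|---|---|---|---|
| any | 0 | 0 | 3.00 | 95.0% | 95.0% |
| 5% | 1 | 0.05 | 3.01 | 94.9% | 94.9% |
| 5% | 3 | 0.15 | 3.07 | 94.4% | 93.8% |
| 10% | 1 | 0.10 | 3.015 | 94.7% | 94.4% |
| 10% | 3 | 0.30 | 3.13 | 92.9% | 90.2% |

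**What f might be.** Section 7.3 expects 10 mimics. Suppose, as an assumption, that 2 to 5 of them stay in untreated tumour groups.

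- Pooled over both untreated groups (45 patients): 2/47 = 4% to 5/50 = 10%.
- All in one untreated group of 22.5: 2/24.5 = 8% to 5/27.5 = 18%.
- Spread evenly over the two types, in a combined group of 45 of one type (treated plus untreated): 1/46 = 2% to 2.5/47.5 = 5%.

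The scale therefore depends on where the mimics fall and on which groups are combined, and 7.3 does not say which combination its n = 45 represents. The rows above show sensitivity; they are not a forecast.

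**Precision lost to group 5.** For an untreated group of 22.5 the half-width is 1.96 × 3/√22.5 = 1.24. Losing 5% (n = 21.4) gives 1.27, and losing 10% (n = 20.25) gives 1.31.

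**The case against.** The strongest reply is that the effect may be negligible. The plan is descriptive, 7.4 specifies no test between tumour types, and coverage falls clearly below 94% at n = 20 only in the row with a shift of a full SD in 10% of the group, a shift with no source in the documents. That stands, and the point does not rest on a demonstrated bias.

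A second reply is that the target may be CNR by classification at enrolment. The background describes the population as known or suspected brain cancer, and 2.7 covers suspected lesions. On that reading a mimic that keeps its enrolment label causes no bias. This is possible, but 1.1.1 speaks of malignancy type, and 7.2 should say so if enrolment classification is meant. It would also not explain calling a pathology-proven glioma a metastasis.

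Three stronger readings might be inferred and are not supported:

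- That patients entered by a neuroradiologist with a neuro-oncologist or radiation oncologist are lost to rule 2. Section 2.7 already requires neurosurgical input for unproven lesions, so this arises mainly if 3.1 is read alone. What remains is inconsistent wording.
- That ill-defined metastases are certain to be dropped. The term well-defined is not explained. Since section 5 requires a measurable diameter and an ROI inside the lesion, it may mean only that the lesion can be delineated.
- That treated patients cannot be typed at all. Their history is an entry criterion in 3.1, so this is a drafting contradiction in 7.2 and not missing information.

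The case of a primary brain tumour with an earlier cancer has no answer in the text.

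**Conclusion.** The point holds as a faulty and partly contradictory definition of the primary strata. Among untreated patients, 7.2 gives wrong assignments for primary brain tumours with an earlier malignancy and for well-defined mimics in patients with a proven solid organ cancer. It may also do so for metastases judged not well-defined. For treated patients, about half of the expected tumour patients, its opening and closing sentences conflict.

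A reader might infer that the reported CNR estimates will be materially biased. The documents do not support that, because neither the misassigned fraction nor the CNR shift is given. Within the assumed values, bias runs from 0 to 0.30 CNR units, and the loss of precision is small. The consequence also depends on the target being actual tumour type, which 1.1.1 favours but does not settle. The wording fault is certain and its numerical effect is not. It should be fixed because the correction is cheap and the groups carry the primary objective.

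**What to change.** In section 7.2:

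1. For the primary analysis, assign type by brain-lesion pathology obtained in routine care and available by data lock; otherwise by the enrolment consensus. Record the likely type at enrolment, before CNR is measured, since 3.1 asks only that the lesion be one type or the other.
2. Remove the no-prior-malignancy condition as a bar to the primary group, and lesion margin as a requirement when the diagnosis is established.
3. Take treated patients' type from their documented tumour history and correct the opening reference to untreated disease.
4. Reserve group 5 for a final non-tumour diagnosis by pathology or chart, confirmed by co-investigators who have not seen the CNR values. Keep unresolved cases at the enrolment consensus, with a flag.
5. Report the current 7.2 grouping as a sensitivity analysis in untreated patients only, because it is not clearly defined for treated ones. Report the basis of diagnosis for each group.
6. Reconcile the specialist wording in 3.1 with 2.7 and 7.2.

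If CNR by enrolment classification is what is intended, state that in 7.2 instead.

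Cost: wording, chart fields for the final diagnosis and its basis, and a short co-investigator confirmation for group 5. There is no added procedure or patient; 7.1.2 already plans to use surgical pathology, where available, for recurrence. The downsides are that assignment may have to wait for pathology, that pathology will be missing for some patients because participation ends at the scan (4.7.1), and that the basis of diagnosis will differ between patients.
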